8.0 EU-1 Page: 74 of 117 Version

10.2.1.3 B - Statistical analysis of time-to-conversion to SR from initiation of dosing up to 90 minutes after initiation of dosing

The cumulative incidence function for the time to conversion from initiation of study drug up to 90 minutes after initiation of dosing will be determined via Kaplan-Meier methods as described in the SAP.

10.2.1.4 B - The proportion of subjects in SR on Day 2

The rhythm status used for the evaluation of this secondary efficacy endpoint is derived from the remote ECG Event Recorder, in which the subject's heart rhythm is recorded. A subject is considered in SR on Day 2 if the remote ECG recording at the intended time shows SR. The variable is set to missing if no evaluable remote ECG recording is available for analysis.

The proportion is estimated by the number of subjects in SR on Day 2, divided by the total number of subjects with available data. The estimate for the proportion and its associated 95% Clopper-Pearson CI will be derived.

B - The proportion of subjects with reduced or no AF symptoms at 30 10.2.1.5 minutes post dose

A subject is considered to have reduced or no AF symptoms at 30 minutes post dose based upon patient-reported outcomes (reported as either 'no symptoms' or 'improved').

The evolution of symptoms (no symptoms, improved, unchanged or worsened) is a categorical variable that will be summarized by the frequency and proportion of subjects within each category. The estimate for the proportion and its associated 95% Clopper-Pearson CI will be derived.

10.2.1.6 B - The proportion of subjects with reduced or no AF symptoms at 60 minutes post dose

A subject is considered to have reduced or no AF symptoms at 60 minutes post dose based on patient-reported outcomes (reported as either 'no symptoms' or 'improved').

The evolution of symptoms (no symptoms, improved, unchanged or worsened) is a categorical variable that will be summarized by the frequency and proportion of subjects within each category. The estimate for the proportion and its associated 95% Clopper-Pearson CI will be derived.

INSTANT Study Clinical Study Protocol

Study no. FLE-002

8.0 EU-1 Page: 75 of 117 Version

10.2.1.7 B - The proportion of subjects with reduced or no AF symptoms at 90 minutes post dose

A subject is considered to have reduced or no AF symptoms at 90 minutes post dose based on patient-reported outcomes (reported as either 'no symptoms' or 'improved').

The evolution of symptoms (no symptoms, improved, unchanged or worsened) is a categorical variable that will be summarized by the frequency and proportion of subjects within each category. The estimate for the proportion and its associated 95% Clopper-Pearson CI will be derived.

10.2.1.8 B - Descriptive statistics of proportion of conversion to SR within 90 minutes after initiation of dosing without AF recurrence requiring electrical or pharmacological cardioversion or rate control intervention up to discharge

This endpoint is derived from the primary efficacy endpoint at 90 minutes after initiation of dosing. The endpoint is met if the subject's AF converts to SR within 90 minutes after initiation of dosing without an alternative therapy and without subsequent AF recurrence up to discharge requiring additional intervention, either by electrical or pharmacological cardioversion or by rate control treatments.

The proportion of subjects that convert to SR without AF recurrence is estimated as the number of subjects who meet the endpoint, divided by the total number of mITT subjects. The estimate for the proportion and its associated 95% Clopper-Pearson CI will be derived.

10.2.1.9 B - The proportion of subjects in SR on Day 5

The rhythm status used for the evaluation of this secondary efficacy endpoint is derived from the remote ECG Event Recorder, in which the subject's heart rhythm is recorded. A subject is considered in SR on Day 5 if the remote ECG recording at the intended time shows SR. The variable is set to missing if no evaluable remote ECG recording is available for analysis.

The proportion is estimated by the number of subjects in SR on Day 5, divided by the total number of subjects with available data. The estimate of the proportion and its associated 95% Clopper-Pearson CI will be derived.

10.2.2 B - Safety analyses

The safety of inhaled flecainide is evaluated by collection of the following measurements performed according to the schedule of study assessments:

- Monitoring of AEs, SAEs, AESIs, and SAESIs;
- Physical examinations;

Study no. FLE-002

Version 8.0 EU-1 Page: 76 of 117

- Vital signs (heart rate, systolic and diastolic blood pressure, respiratory rate and oxygen saturation);

- Routine ECGs or 10-second printouts of the telemetry rhythm strip performed for safety purposes are printed and reviewed on-site;
- Continuous telemetry;
- Pulmonary function by lung auscultation and oxygen saturation;
- Clinical local laboratory assessment (incl. hematology, comprehensive metabolic and coagulation panel).

Safety analyses will be performed and the results summarized in the safety population. The verbatim terms used in the eCRF by Investigators to identify AEs are coded using the Medical Dictionary for Regulatory Activities (MedDRA) by System Organ Class (SOC) and Preferred Term. All reported AEs with onset during the treatment phase or that were already present but worsened either in intensity or frequency following the treatment (i.e., TEAEs) are included in the analysis. The incidence and percentage of subjects with at least 1 occurrence of a Preferred Term are included, according to the most severe grade using a 3-point scale (mild, moderate, severe). The number of events per Preferred Term is summarized. Causality (relationship to study treatment) is summarized separately. The incidence and frequency of TEAEs (including TESAEs and AESI) are summarized according to SOC and Preferred Terms. Durations of events are determined and included in listings, along with the action taken and outcome.

10.2.2.1 B - Clinical laboratory evaluation analyses

Laboratory data are summarized by type of laboratory test. Reference ranges and clinically significant abnormal results are depicted in the summary of clinical local laboratory data, as described in the SAP. Descriptive statistics are used for each laboratory parameter at screening (Day 1) and at discharge.

10.2.2.2 B - Vital signs analyses

Vital signs measurements and their change from baseline are summarized for the safety population at each scheduled time point using descriptive statistics. Time course of the changes is summarized in tables and also represented graphically.

10.2.2.3 B - Physical examination analyses

Physical examination findings are summarized at screening and presented in subject listings.

10.2.3 B - Pharmacokinetic / Pharmacodynamic analyses

Table 2 describes the PK parameters to be calculated for plasma flecainide concentrations. The PK analysis is performed in all enrolled subjects who inhaled the full assigned dose (PK population).

INSTANT Study

Clinical Study Protocol

Study no. FLE-002

Version 8.0 EU-1 Page: 77 of 117

Table 2 - Pharmacokinetic parameters to be calculated for plasma flecainide

AUC ₀₋₁₀ :	The area under the plasma concentration versus time curve from the start
	of dosing (time zero, T ₀) to 10 minutes after initiation of dosing
AUC ₀₋₉₀ :	The area under the plasma concentration versus time curve from the start
	of dosing (time zero, T ₀) to 90 minutes after initiation of dosing
C _{max} :	The peak (maximum) plasma concentration prior to the start time of any
	alternate pharmacological therapy, is to be obtained directly from the
	plasma concentration time profile
t _{max} :	The time to C_{max} (from the time of end of dosing) is obtained. If t_{max} is
	reached prior to the end of dosing, a negative value will be reported.
t _{1/2} distribution:	The distributive half-life is calculated by the equation $t_{1/2} = \ln(2)/k_{dist}$

The effects of inhaled flecainide on the following ECG intervals is measured:

Heart rate (HR)

• RR interval

PR interval

QRS duration

QTcF duration

JTc duration (QTc-QRS)

PK and PD data are analyzed in an exploratory manner and summarized descriptively. Time course of the changes is summarized in tables and also graphically represented. Details are given in a PK/PD analysis plan. The results of these analyses are presented in a separate report.

10.3 B - Sample size determination

In Part B, the estimated sample size of 25 mITT subjects for the 120 mg dose cohort is based upon the evaluation of the following statistical hypotheses using an exact binomial test, H_0 : $\rho = 20\%$ versus H_A : $\rho > 20\%$ ($\alpha = 0.05$).

Given the actual conversion rate for the Part A 120 mg dose cohort is 44%, a sample size of 25 subjects has 84% power to reject the null hypothesis (H_0) in favor of the alternative (H_A) with a one-sided significance level of 0.05. The null hypothesis is rejected when at least 9 subjects' AF converts to SR within 60 minutes after initiation of dosing.

If 9 subjects' AF converts to SR, the resulting conversion rate is 36% with a 90% exact binomial confidence interval of [20.24%, 54.39%]. If 9 or more subjects' AF converts to SR, the lower bound of the 90% exact binomial confidence interval will be greater than 20.24%. When the lower bound of the 90% confidence interval for conversion rate is greater than 20%, there is sufficient support for the rejection of the null hypothesis in favor of the alternative.

It is expected approximately 20 subjects will participate in the Handheld Echo Sub-Study in Part B and the Part C Medically-Led Cardioversion Study; however, the Sub-Study does not have a minimum or maximum enrollment target.

Study no. FLE-002

Version 8.0 EU-1 Page: 78 of 117

XII. Study protocol (Part C - EU only): Medically-Led Cardioversion and Patient-Led Under Medical Supervision Cardioversion Studies

2 C - Study objectives

All Part C objectives are exploratory:

- To explore the feasibility of patient-led self-administration of flecainide acetate inhalation solution in a hospital setting under medical supervision
- To explore the PK/PD of flecainide acetate inhalation solution in subjects with recent onset of paroxysmal AF for patient-led administration relative to medically-led administration, including resumption of SR
- To explore the feasibility of implementing a portable cardiac ultrasound (HHE) at screening in an emergent setting

3 C - Study design

Part C is conducted in Europe only. Part C comprises two distinct studies, a Medically-Led Cardioversion Study (procedures are identical to those in Part B) and a Patient-Led Under Medical Supervision Cardioversion Study (procedures include the subject self-preparing and self-administering the study drug under medical supervision in the clinic).

Subjects with recent-onset AF who have not been previously treated with flecainide acetate inhalation solution will first be enrolled into the Medically-Led Cardioversion Study to determine eligibility for rollover participation in the Patient-Led Under Medical Supervision Cardioversion Study.

Subjects who first participate in the Medically-Led Cardioversion Study whose AF converts to SR with flecainide acetate inhalation solution and who did not experience any serious AE(s), serious AESIs, or difficulties or issues with inhalation (in the opinion of the investigator) are then eligible for the Patient-Led Under Medical Supervision Cardioversion Study.

Subjects from Part A and Part B who already had a previous AF episode converted to SR with flecainide acetate inhalation solution and who did not experience any serious AE(s), serious AESIs, or difficulties or issues with inhalation (in the opinion of the investigator) are also eligible for the Patient-Led Under Medical Supervision Cardioversion Study. These subjects do not need to participate in the Part C Medically-Led Cardioversion Study prior to proceeding into the Patient-Led Under Medical Supervision Cardioversion Study.

The schematic for subject flow into Part C is described in

Figure 5.

[figure not shown]
INSTANT Study

Clinical Study Protocol

Study no. FLE-002

Version 8.0 EU-1 Page: 79 of 117

Figure 5. Schematic for Part C: 120 mg Dose

For both studies in Part C, subjects receive a repeat dose regimen of 120 mg eTLD (2 x 60 mg) FlecIH-103 inhalation solution. The dose regimen is described in Section 5.1 B. The study design for Part C is described in **Figure 6**.

The Patient-Led Under Medical Supervision Cardioversion Study requires subjects to return to the clinic for training, pass an assessment of their ability to self-administer the study drug, and then return to the clinic within 48 hours of the onset of symptoms when they experience a recurrent episode of paroxysmal AF to self-administer the study drug. Subjects may return and self-administer study drug for one recurrent episode of AF.

[figure not shown]
Figure 6. Part C Study Design

Study no. FLE-002

Version 8.0 EU-1 Page: 80 of 117

^{*}Potentially eligible patients from Part A, Part B, and the Medically-Led Cardioversion Study in Part C may provide Informed Consent for the Part C Patient-Led Under Medical Supervision Cardioversion Study.

4 C - Study population

Part C does not have an enrollment target; enrollment will continue in the Part C Medically-Led Cardioversion Study at the discretion of the Sponsor to support rollover participation in the Part C Patient-Led Under Medical Supervision Cardioversion Study.

Subjects to be included in the Patient-Led Under Medical Supervision Cardioversion Study must be re-checked for eligibility according to the same criteria in Part B (Section 4.1 B and 4.2 B) prior to each treatment of a recurrent AF episode with the study drug. Safety labs and a symptom-driven physical examination may be performed at the discretion of the PI (e.g., due to changes in recent medical history); except for those required to confirm the subject's eligibility, which must be performed.

If a subject is not eligible, they may be treated as per institutional standard of care and return again if the future for a different recurrent episode of AF.

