Feasibility was assessed in terms of the following performance characteristics:

- a) Rates of study enrollment, screen failures and refusals of IC:
- b) The rate of technically successful administration of study inhalation regimens;
- c) Successful capture of study data according to the schedule of study assessments;
- d) Successful remote capture of AF-status at follow-up contacts

Conversion of AF to SR and safety/tolerability were compared in an exploratory manner.

Study endpoint(s) PART B

The primary efficacy endpoint is the proportion of subjects whose AF converted to SR by inhaled flecainide within 90 minutes after initiation of dosing. For the definition of the endpoint *conversion to SR* refer to Section 10.2.1.1 B.

Secondary efficacy endpoints include:

 The proportion of subjects with C_{max} values ≥ 200 ng/mL (e.g., 200, 300, 400, and 500 ng/mL) post inhalation with inhaled flecainide (excluding plasma levels associated with IV flecainide infusion) whose AF converted to SR by

INSTANT Study Clinical Study Protocol

Study no. FLE-002

Version 8.0 EU-1 Page: 15 of 117

inhaled flecainide within 90 minutes after initiation of dosing.

- The time to conversion of AF to SR from initiation of dosing up to 90 minutes after initiation of dosing;
- The proportion of subjects in SR on Day 2;
- The proportion of subjects with reduced or no AF symptoms at 30 minutes post dose;
- The proportion of subjects with reduced or no AF symptoms at 60 minutes post dose;
- The proportion of subjects with reduced or no AF symptoms at 90 minutes post dose;
- The proportion of subjects who had their AF converted to SR by inhaled flecainide within 90 minutes after initiation of dosing and had no AF recurrence, requiring electrical or pharmacological cardioversion or rate control intervention, up to discharge;
- The proportion of subjects in SR on Day 5.

Time to conversion will be reported in statistical analyses from both initiation of dosing and completion of dosing.

The secondary safety endpoint is the incidence of treatment emergent serious adverse events of interest for flecainide.

Exploratory endpoints (HHE):

- Proportion of subjects for whom capture and assessment of a diagnostic echocardiogram using a HHE at screening was successful
- Percent of subjects who are considered ineligible for enrollment as a result of the HHE assessment
- Time from HHE administration to availability of HHE report/results

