INSTANT Study Clinical Study Protocol

Study no. FLE-002

Version 8.0 EU-1 Page: 17 of 117

the Sponsor to support rollover participation in the Part C Patient-Led Under Medical Supervision Cardioversion Study (refer to description above).

All subjects enrolled and treated with study drug will be analyzed within the safety population. For the modified intention-to-treat population (mITT), for any subject who was not in AF at the time of dosing and who does not complete inhalation of the full assigned dose will be replaced to keep the sample size needed.

In Part B, the estimated sample size of 25 subjects for the 120 mg dose cohort is based upon the evaluation of the following statistical hypotheses using an exact binomial test,

$$H_0$$
: $\rho = 20\%$ versus H_A : $\rho > 20\%$ ($\alpha = 0.05$).

Given the actual conversion rate for the Part A 120 mg dose cohort (FlecIH-103 inhalation solution) is 48%, a sample size of 25 subjects has at least 92% power to reject the null hypothesis (H_0) in favor of the alternative (H_A) with a one-sided significance level of 0.05. The null hypothesis is rejected when at least 9 subjects' AF converts to SR within 90 minutes after initiation of dosing.

For example, with 25 subjects enrolled in Part B, if 9 of them have their AF converted to SR, the resulting conversion rate is 36% with a 90% exact binomial confidence interval of [20.24%, 54.39%]. If 9 or more subjects' AF converts to SR, the lower bound of the 90% exact binomial confidence interval will be greater than 20.24%. When the lower bound of the 90% confidence interval for conversion rate is greater than 20%, there is sufficient support for the rejection of the null hypothesis in favor of the alternative.

It is expected approximately 20 subjects will participate in the HHE Sub-Study in Europe (Part B and the Part C Medically-Led Cardioversion Study); however, the HHE Sub-Study does not have a minimum or maximum enrollment target.

Statistical analyses

INSTANT Study

Clinical Study Protocol

Study no. FLE-002

Version 8.0 EU-1 Page: 18 of 117

PART A:

The main feasibility, efficacy and safety parameters were presented in a descriptive manner. Data on PK, PD and other assessments were presented in a similar manner.

PART B:

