Doses of 30 mg (1 x 30 mg), 60 mg (2 x 30 mg), and 90 mg (2 x 45 mg) and 120 mg (2 x 60 mg) have been under evaluation in this study based on PK and PD data (QRS prolongation) from FLE-001 and FLE-003 showing that doses \geq 30 mg had the potential to convert AF to SR. Part A concluded after enrolling 101 subjects, as follows: 10 subjects treated with 30 mg eTLD, 22 subjects treated with 60 mg eTLD, 21 subjects treated with 90 mg eTLD, and 48 subjects treated with 120 mg (19 with FlecIH-102 and 29 with FlecIH-103. Enrollment in the 120 mg dose cohort was completed on 05Mar2020 and Part A was concluded. The rate of conversion from AF to SR observed to date for the dose cohorts is as follows: 30 mg, 1/10 (10%); 60 mg, 6/18 (33%; 2 subjects were excluded from analysis as they were not in AF at time of dosing); and 90 mg, 7/21 (33%); For the 120 mg dose, the conversion rate was 7/17 (41%) for the FlecIH-102 cohort (2 subjects were excluded from efficacy analysis because they did not receive the full dose of study drug) and 13/27 (48%) for the FlecIH-103 cohort (2 subjects were excluded from the efficacy analysis because they did not receive the full dose of study drug).

The majority of subjects had AEs that were mild in severity and the most commonly reported AEs were those associated with the inhalation route of administration, e.g., cough and throat irritation. All non-serious AEs of bradycardia and hypotension were minor, transient and resolved without drug treatment. A total of four subjects experienced serious AEs (SAEs) that were considered possibly related to study drug by the Investigator or Sponsor. The SAEs considered related to inhaled flecainide included the following: two cases of prolonged sinus pauses at the time of conversion of AF to SR (one mild and one moderate, as per the Investigators), one case of bradycardia (severe, as per the Investigator), and one case of atrial flutter with 1:1 conduction with fast ventricular response (severe, as per the Investigator). All SAEs were transient in nature, resolved without intervention, and had no sequelae.

Based on the feasibility, safety, tolerability and efficacy results from Part A using the FlecIH-103 inhalation solution, Part B and Part C of the study will use the 120 mg dose of flecainide to further evaluate the cardioversion of recent onset AF.

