7.5 B - Study endpoint(s)

7.5.1 B - Primary endpoint

The primary efficacy endpoint is the proportion of subjects whose AF converted to SR by inhaled flecainide within 90 minutes after initiation of dosing. Conversion of AF to SR is defined as the presence of SR lasting for at least 1 minute.

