10.2.1.1 B - Statistical analysis of the primary efficacy endpoint

The endpoint of conversion to SR is defined as the presence of SR, derived from the AECG, lasting for at least 1 minute. The first conversion to SR that lasts for at least 1 minute is referred to as the index conversion. Any conversion not lasting for at least 1 minute is not considered an index conversion.

The conversion rate (%) of recent onset of AF to SR, within 3 hours, ranges from 2-14% spontaneously²² and with placebo^{51, 52} approximately $16\%^3$. In more recent studies such as those with vernakalant, the reported placebo conversion rate was ~5 $\%^4$. For this study, we have selected a somewhat higher placebo conversion rate of 20%. In order to statistically evaluate whether the proportion of subjects whose AF converted to SR by inhaled flecainide within 90 minutes after initiation of dosing is > 20%, the following hypotheses are evaluated at a one-sided significance level of 0.05:

 $H_0: \rho = 20\%$

The one-sided alternative hypothesis is:

 $H_A: \rho > 20\%$

The null hypothesis is tested with the use of an exact binomial test. A 90% Clopper-Pearson confidence interval is computed for the proportion of subjects who met the primary endpoint. If the lower bound of the 90% confidence interval is > 20% then the null hypothesis is rejected in favor of the alternative, i.e. there is sufficient evidence to conclude the percentage of subjects AF converting to SR is > 20%.

10.2.1.2 B - Statistical analysis of proportion of subjects who convert within 90 minutes after initiation of dosing and have C_{max} values ≥ 200ng/mL (e.g., 200, 300, 400, and 500 ng/mL)

This endpoint is defined as the number of subjects who meet the endpoint criteria, divided by the total number of subjects included in the analysis. The estimate for the conversion rate and its associated 95% Clopper-Pearson Cls will be derived.

For the purpose of this study, C_{max} is defined as the peak plasma level of flecainide prior to administration of any alternative pharmacological agent (e.g., oral flecainide).

INSTANT Study Clinical Study Protocol

Study no. FLE-002

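### Protocol 10.3 B gives the wrong Part A rate, power and conversion window for the Part B test: 44%, 84% and 60 minutes, against 48%, at least 92% and 90 minutes in the synopsis

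*Protocol*

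**What the plan says.** Two places in the same protocol version describe the sample size for Part B. They agree on the test (exact binomial, null rate 20%, one-sided 0.05), the number of subjects (25), the rejection count (9 or more) and the worked 90% interval at 9/25. They differ on three figures.

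| Item | Synopsis, planned sample size | Section 10.3 B |
|---|---|---|
| Part A rate called actual | 48%, FlecIH-103 named | 44%, no formulation named |
| Power | at least 92% | 84% |
| Window for the rejection count | 90 minutes | 60 minutes |

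- **Section 10.3 B:** "Given the actual conversion rate for the Part A 120 mg dose cohort is 44%, a sample size of 25 subjects has 84% power". Its rejection rule counts a subject when "AF converts to SR within 60 minutes after initiation of dosing".
- **Synopsis:** the rate "is 48%, a sample size of 25 subjects has at least 92% power", and the rule counts a subject when "AF converts to SR within 90 minutes after initiation of dosing".

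Other sections bear on which version is right:

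- Protocol 1.4 reports Part A conversion as "13/27 (48%) for the FlecIH-103 cohort", which is the formulation used in Part B.
- Protocol 7.5.1 B: "The primary efficacy endpoint is the proportion of subjects whose AF converted to SR by inhaled flecainide within 90 minutes after initiation of dosing".
- Protocol 10.2.1.1 B, which defines the primary test, asks "whether the proportion of subjects whose AF converted to SR by inhaled flecainide within 90 minutes after initiation of dosing is > 20" percent.
- SAP 6.2.1 and 9.2.1 give the same 90-minute endpoint.

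**The concern.** Section 10.3 B is where a reader looks for the planning rate, the power and the decision rule of the only formally tested endpoint. Read alone, it gives a lower planning rate, a lower power and a window that is not the primary endpoint. The window matters most, because it decides which conversions count towards the nine.

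The rule also has a downstream use. Protocol 10.2 B allows the Part A and Part B FlecIH-103 cohorts to be combined only if Part B meets its significance criterion and does not differ substantially from Part A. SAP 9.3 says that pooling went ahead. The criterion is written two ways in the current protocol. The list of differences from the protocol in SAP section 10 does not mention the conflict, and SAP 7.1 does not restate the Part B power or rule.

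**Working it through.** **Inputs.** From both the synopsis and 10.3 B: n = 25, null rate 0.20, one-sided alpha 0.05, reject at X ≥ 9. Planning rates: 0.48 (synopsis) and 0.44 (10.3 B). From Protocol 1.4, Part A 120 mg: FlecIH-102 converted 7 of 17 evaluable (19 treated), and FlecIH-103 converted 13 of 27 evaluable (29 treated).

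**Formula.** P(X ≥ c | p) = Σ from k = c to 25 of C(25, k) p^k (1 − p)^(25 − k).

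**1. Cut-off.** P(X ≥ 8 | 0.20) = 0.1091, above 0.05. P(X ≥ 9 | 0.20) = 0.0468, below 0.05. So 9 is the correct critical value. The 90% Clopper-Pearson interval for 9/25 is 20.24% to 54.39%, as both places state. For 8/25 the lower bound is 17.03%, below 20%, which confirms the cut-off.

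**2. Power.** Both stated figures reproduce from their own rates:

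- at 0.44 (10.3 B): 0.8431, stated as 84%;
- at 0.48 (synopsis): 0.9205, stated as at least 92%;
- at 13/27 unrounded: 0.9226.

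The gap is 0.9205 − 0.8431 = 0.0774, or 7.7 percentage points. The conflict lies in the inputs and not in the calculation.

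**3. Is 44% any Part A 120 mg rate in the protocol?**

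| Group | Evaluable | Treated |
|---|---|---|
| FlecIH-102 | 7/17 = 41.2% | not needed for 10.3 B |
| FlecIH-103 | 13/27 = 48.1% | 13/29 = 44.8% |
| Both formulations | 20/44 = 45.5% | 20/48 = 41.7% |

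None rounds to 44%. A count of 12/27 would (44.4%, power 0.854), and it is one conversion fewer than 13/27, but the documents report no such count. It is only a reason to ask which window each rate refers to.

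**4. Window.** Ninety minutes from the start of dosing appears in the synopsis endpoint and rejection rule, Protocol 7.5.1 B and 10.2.1.1 B, and SAP 6.2.1 and 9.2.1. Sixty minutes as the conversion window for this test appears only in 10.3 B.

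**5. Illustration of what the window could change.** The documents do not give the share of conversions that come after 60 minutes, so the late share f below is assumed. A subject converted by 60 minutes is also converted by 90, so the two counts give different verdicts with probability P(X ≥ 9 | 0.48) − P(X ≥ 9 | 0.48(1 − f)).

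| Assumed f | 60-minute rate | Difference |
|---|---|---|
| 0% | 0.480 | 0 |
| 2% | 0.4704 | 0.9205 − 0.9053 = 0.015 |
| 5% | 0.456 | 0.9205 − 0.8786 = 0.042 |
| 10% | 0.432 | 0.9205 − 0.8230 = 0.0975 |

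**The case against.** The strongest reply is that nothing operative depends on 10.3 B. Section 10.2.1.1 B defines the primary test at 90 minutes, and N, the cut-off, alpha and the worked interval are the same in both versions. Both powers exceed 80%, and 84% understates the power. All of this stands, and it limits the consequence. It does not make 10.3 B correct: a power and a rejection rule are figures that others will cite, and these rest on a rate and a window that the rest of the protocol contradicts.

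A second reply is that the Part B verdict was almost certainly taken at 90 minutes. SAP 6.2 ties the endpoints reported for Part B to Protocol 7.5 B, which says 90. SAP 9.3 attributes the pooling of Parts A and B to a homogeneity test and does not mention the count of nine, and the pooling across Parts A, B and C involves no formal test. This is fair, and nothing in the documents suggests a 60-minute analysis. But the Part B report and the Part B SAP (V4.0 and V4.1) are not among the documents, so the point is probable and not confirmed. One sentence from the sponsor would settle it.

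A third reply is that 44% might be a genuine 60-minute rate, which would make 10.3 B coherent older text. SAP 9.2.3.3 shows that an earlier protocol version timed the satisfaction questions at 60 minutes, so carry-over is possible, but that section concerns a questionnaire and not conversion. Neither the synopsis nor Protocol 1.4 gives a window for the 48%. This is a good reason to ask for the windows. It does not rescue 10.3 B, because a 60-minute rate would still be the wrong basis for a 90-minute test.

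**Conclusion.** The concern holds. Section 10.3 B conflicts with the synopsis on the rate, the power and the window of the same test, and the other sections identify 10.3 B as the one in error. It understates the power by 7.7 points (84.3% against 92.0%) and attaches the rejection rule to 60 minutes when the primary endpoint is at 90.

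The defect must be corrected because a power and a decision rule are wrong as written, but its reach is limited: the sample size, the cut-off of 9, alpha and the primary analysis are unaffected. Taking 48% as the planning rate for a 90-minute test assumes that the 13/27 was itself counted over 90 minutes, which the documents do not state. The late-share figures are an illustration on assumed inputs and say nothing about what happened in Part B.

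**What to change.** In Protocol 10.3 B, replace the three figures: 48% (13/27, Part A 120 mg FlecIH-103), 92% power, and 90 minutes from the start of dosing. Leave N = 25 mITT subjects, the cut-off of 9, alpha and the interval of 20.24% to 54.39% as they are.

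Part B has already been reported, so the study report should also:

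1. note the error in 10.3 B;
2. confirm the window used for the Part B verdict that preceded pooling;
3. state the window to which the 48% Part A rate refers.

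If no further amendment is planned, the study report note carries the correction. The cost is three figures in one paragraph and a short note, with no change to design, data collection or analysis.
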